16.4 Study Sample Size, Decision Rule, and Study Duration

16.41 *Sample size:* This study requires 153 evaluable women for the primary endpoint analysis. We anticipate accruing 15 additional patients to account for ineligibility, cancellation, major treatment violation, or other reasons. The maximum projected accrual is therefore 168 women, and we expect a maximum of 60 and a minimum of 40 women within each cohort (photon, proton, and brachytherapy).

16.42 *Study Decision Rule and Operating Characteristics:* Olivotto et al. previously reported interim cosmetic and toxicity results from a randomized trial comparing APBI using 3D-CRT versus WBI. In this study, the same 3DCRT dose and fractionation was used as in the previously discussed NSABP B-39/RTOG 0413 randomized controlled trial comparing 3DCRT or brachytherapy APBI with WBI. At 3 years, the percentage difference in patients with adverse cosmesis in the APBI arm compared to baseline by trained nursing assessment was 10.6%. The proposed analysis is to compute the percentage difference in patients with adverse cosmesis (fair or poor cosmesis) at 3 years compared to baseline. A one-sided 95% confidence interval (with the upper bound of the interval) was computed, by assuming the difference in adverse cosmesis rate at 3 years compared to baseline is 10%, and the distance from 10% to the upper bound of the CI is 4%. The decision rule would be of the following:

- If the upper bound of the one-sided CI for the difference of adverse cosmesis rate lies above 14%, then recommend no further investigation and conclude that there is no sufficient evidence to accept the adverse cosmesis rate of 3 fraction accelerated APBI.
- If the upper bound of the one-sided CI for the difference of adverse cosmesis rate lies below 14%, then recommend further investigation and conclude the increase in 3-year adverse cosmesis rate of 3 fraction accelerated APBI is potentially acceptable.

The study operating characteristics is determined as the chance of declaring that APBI warrants further study, assuming a true value for the difference in adverse cosmesis rate at 3 years compared to baseline for APBI. The table below shows the operating characteristics of this trial with 153 patients and the decision rule given above.

True increase in adverse cosmesis rate at 3 years compared to baseline	Probability of concluding PBI warrants further study
5%	98.4%
10%	72.8%
15%	48.6%
20%	29.8%

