16.44 Accrual time and Study duration: Since 10/1/2012 patients have been treated with brachytherapy APBI using an 8 or 10 fraction regimen and prospectively followed as part of a clinical registry at the Mayo Clinic in Rochester, MN. Patient interest in the procedure has steadily increased, and in the last 3 months, 13 patients have been treated (median 4.3 patients per month), all of whom would be eligible for this study. A similar to increased level of accrual of brachytherapy patients is anticipated during the course of this study as familiarity with this procedure amongst surgical and radiation oncology providers rises. With the addition of the photon APBI alternative for patients, we anticipate an accrual rate of 5 patients per month for the first year until the opening of

the Mayo proton facility, after which an accrual of 8 patients per month is anticipated. Therefore, the accrual period for this study is expected to be approximately 3 years. We plan to open this study at the Mayo Clinic in Scottsdale and Jacksonville which will further enhance accrual. Final analysis may begin approximately 5 years after the trial begins, i.e. as soon as the last patient registered has been observed for at least 24 months. A maximum of 60 patients and a minimum of 40 patients will be enrolled per treatment arm.

16.5 **Primary Analysis:** The primary analysis will be to estimate the percentage difference in patients with adverse cosmesis (fair or poor cosmesis) at 3 years compared to baseline. All patients meeting the eligibility criteria who have signed a consent form and started treatment will be in the primary analysis. The percentage difference in patients with adverse cosmesis will be estimated using a binomial estimator (number of women who had an adverse cosmesis event at 3 years minus number of women who had an adverse cosmesis event at baseline, and then divided by total number of women in the primary analysis) and a 95% exact binomial confidence interval. As mentioned above, the following decisions will be made based on the 95% CI:

- ***The upper bound of the 95% CI lies below 14%:*** APBI adverse cosmesis is acceptable.
- ***The upper bound of the 95% CI lies above 14%:*** No evidence to show that APBI adverse cosmesis is acceptable.

16.6 **Secondary Analyses**

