Mounting evidence also suggests that genetic variation may play an important role in determining susceptibility to radiation toxicity.⁷⁰ Radiogenomics is an emerging field aimed at studying genetic differences associated with variability in the effectiveness and toxicity of radiation.⁶¹ We plan to use a candidate gene approach⁶¹ to investigate the association of single nucleotide polymorphisms (SNPs), previously correlated with radiation normal tissue toxicity, with adverse cosmesis following 3 fraction APBI. For example, in addition to TGF- β 1, SNPs in the XRCC1 (codon 241) and XRCC1 (codon 399) genes, the protein products of which function in the DNA repair pathways of based excision repair and homologous recombination, respectively, have been correlated with increased risk of subcutaneous fibrosis following breast cancer radiotherapy. [REDACTED]

[REDACTED] laboratory at the Mayo Clinic has used a genome-wide association approach in human lymphoblastoid cell lines to identify radiation response biomarkers. C13orf34, MAD2L1, PLK4, TPD52, and DEPDC1B were identified and functionally validated as modifiers of radiation response. These promising findings, however, require further clinical validation.^{61,71}

The final design of these future genomic and proteomic studies will depend on the event rate observed in the trial, cost and state of technology at the time of per protocol cosmetic evaluation of all patients enrolled. They may occur as part of a meta-analyses of patients treated with hypofractionated breast cancer radiotherapy from other institutions.

Over Accrual: If more than the target number of patients are accrued, the additional patients will not be used to evaluate the stopping rule or used in any decision making processes; however, they will be included in final endpoint estimates and confidence intervals.

16.8 Results Reporting on ClinicalTrials.gov: At study activation, this study will have been registered within the “ClinicalTrials.gov” website. The Primary and Secondary Endpoints along with other required information for this study will be reported on ClinicalTrials.gov. For purposes of timing of the Results Reporting, the initial estimated completion date for the Primary Endpoint of this study is 5 years after the study opens to accrual. The definition of “Primary Endpoint Completion Date” (PECD) for this study is at the time the last patient registered has been followed for at least 3 years.

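### The three-year accrual forecast in section 16.44 does not follow from its own rates, and the final-analysis and primary-completion timings imply different accrual periods

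*Combined protocol and SAP*

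**What the plan says.** Section 16.41 sets the size: "This study requires 153 evaluable women for the primary endpoint analysis", and, with 15 more for losses, "The maximum projected accrual is therefore 168 women". It expects between 40 and 60 women per technique, and 16.44 repeats those limits.

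Section 16.44 gives the rates: "we anticipate an accrual rate of 5 patients per month for the first year until the opening of" the proton facility, "after which an accrual of 8 patients per month is anticipated". It then draws the conclusion that "the accrual period for this study is expected to be approximately 3 years". It adds: "We plan to open this study at the Mayo Clinic in Scottsdale and Jacksonville which will further enhance accrual". It allows the final analysis at roughly 5 years from the start, which it equates with the point "as soon as the last patient registered has been observed for at least 24 months".

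Section 16.8 says that "the initial estimated completion date for the Primary Endpoint of this study is 5 years after the study opens to accrual", and defines that completion as the last registered patient having been followed for at least 3 years. Sections 16.1, 16.2 and 16.5 all place the primary endpoint, change in adverse cosmesis from baseline, at 3 years.

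**The concern.** The accrual period is offered as a deduction from two rates, and the deduction fails by a margin that rounding cannot explain. The forecast also feeds the analysis timing in the same paragraph. There, 5 years and 24 months of observation on the last woman are treated as the same moment, which is true only if accrual takes 36 months. Section 16.8 gives 5 years as well but needs 36 months of follow-up, which leaves about 24 months for accrual. The two sections therefore reach the same date from different accrual periods.

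What is at stake is when the primary analysis can properly be run. If the 24-month condition were used as the trigger while accrual ran at the stated rates, more than half of the women would not yet have reached the time point that defines the primary endpoint.

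**Working it through.** **Inputs.** Maximum accrual 168 and evaluable target 153 (16.41); 5 per month for 12 months, then 8 per month (16.44); at most 60 per technique (16.41, 16.44); 24 months of observation for the final analysis (16.44); 3 years of follow-up for completion (16.8). Follow-up is counted from registration.

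**Accrual time.** T = 12 + (N − 5 × 12)/8 months.

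- N = 168: 12 + 108/8 = 25.5 months.
- N = 153: 12 + 93/8 = 23.6 months.
- N = 180 (three full groups of 60): 12 + 120/8 = 27.0 months.

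No target size in the plan gives 36. Run the other way, 36 months gives 60 + 24 × 8 = 252 women, which is 84 above the maximum. For 168 women to take 36 months, the rate after year 1 would have to be 108/24 = 4.5 per month. A flat 5 per month throughout gives 168/5 = 33.6 months, close to 3 years, but only by ignoring the stated rise to 8.

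**Dates.** Accrual plus follow-up on the last woman:

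| Accrual | + 24 months | + 36 months |
|---|---|---|
| 36 months (as stated) | 60 (5.0 years) | 72 (6.0 years) |
| 25.5 months (stated rates) | 49.5 (4.1 years) | 61.5 (5.1 years) |

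The 16.44 analysis date is the top-left cell. The 16.8 completion date matches the bottom-right cell. They sit in different rows and different columns.

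**Women short of 3 years when the 24-month condition is met.**

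- Stated rates, month 49.5: women registered by month 49.5 − 36 = 13.5 have 3 years, which is 60 + 1.5 × 8 = 72. The other 168 − 72 = 96 (57%) do not.
- Allowing the 3-month early window for annual visits in 18.1, the cut-off is month 16.5: 60 + 4.5 × 8 = 96 women have a score and 72 (43%) do not.
- If accrual really takes 36 months (assumed 4.5 per month after year 1), at month 60 the cut-off is month 24: 60 + 12 × 4.5 = 114 women have 3 years and 54 (32%) do not.

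**Effect of the cap of 60 per technique.** Brachytherapy and photon together can supply at most 120 women, so proton must supply at least 48. Reaching 168 at month 25.5 needs 48/13.5 = 3.6 proton patients per month from month 12. The plan gives no rates for photon or proton. If the step from 5 to 8 is read as 3 proton patients per month (an assumption), the earliest finish is 12 + 48/3 = 28 months, reached for example with brachytherapy and photon at 2.5 each. Other assumed splits take longer:

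- Brachytherapy 3.67, photon 1.33, proton 3: brachytherapy fills at month 16.4 and proton at month 32; photon reaches 48 at month 36, for a total of 168.
- Brachytherapy 4.3, photon 0.7, proton 3, with nobody changing technique: photon reaches 48 at 48/0.7 = 68.6 months.

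**The case against.** The best defence is the cap. Once it applies, the overall rates cannot be carried forward unchanged, and some technique mixes do give 36 months, as the working shows. This stands to the extent that 25.5 months cannot be put forward as the true duration, and 3 years cannot be called impossible. It does not rescue the deduction: 16.44 derives 3 years from the overall rates, never cites the cap as the reason, and states no mix. The extra sites would shorten accrual, not lengthen it.

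A second defence is that this is a forecast, worded as such, and that both timing rules are tied to follow-up of the last patient. The 24 months is also worded as a minimum, so nothing forces an early analysis. That is fair and limits the weight of the point. The plan nevertheless permits a final analysis on a follow-up condition shorter than its primary endpoint.

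A reader might infer that the 5-year dates are wrong because the accrual figure is wrong. The documents do not support this. Section 16.8 cites no accrual period, and correcting accrual to 25.5 months puts completion at 61.5 months, in line with its 5 years. Five years is also about right for the final analysis in 16.44 once both its accrual figure and its follow-up condition are corrected.

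**Conclusion.** The point holds as an internal inconsistency in planning and timing. At the stated overall rates, accrual of 168 women takes 25.5 months, 10.5 fewer than the 36 stated. The rates, the 3-year accrual, the 24-month analysis condition and the 3-year completion definition cannot all stand together. The practical consequence is that, at the stated rates, the 24-month condition is met at month 49.5 with 96 of 168 women short of 3 years.

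This rests on constant rates, a switch to 8 per month at month 12, and follow-up counted from registration. Under the cap the duration depends on a mix that the plan does not state; 28 months is the earliest if proton runs at 3 per month. A reader might also take the figure of about 69 months as a prediction of severe delay. It is not one: it extends a three-month registry rate from a single site, obtains the photon rate by subtraction, and assumes that no woman changes technique.

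Sample size, error rates and the 14% decision threshold are unaffected.

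**What to change.** In 16.44, choose one of two consistent sets of figures:

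1. Restate accrual as about 26 months at the stated overall rates, or about 28 months or more if the cap of 60 binds, and give the assumed technique mix. Keep primary completion in 16.8 at about 5 years (25.5 + 36 = 61.5 months; 28 + 36 = 64 months).
2. Keep 3 years, restate the rate after year 1 as about 4.5 per month, and move both the final analysis in 16.44 and the completion date in 16.8 to about 6 years (36 + 36 = 72 months).

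In both cases, replace the 24-month observation condition with completion of the last patient's 3-year cosmesis assessment, so that 16.44 agrees with 16.5 and 16.8.

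The cost is one paragraph and, under the second option, one date in 16.8. No extra patients are needed. The second option moves the forecast analysis date about a year later than the plan now states.

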16.0 Statistical Considerations and Methodology

- 16.1 Overview: This is a single arm phase II study evaluating the rate of adverse cosmesis (defined as fair or poor cosmesis) at 3 years, compared to baseline, of 3 fraction accelerated APBI. For the analysis of the primary endpoint, patients will be pooled across the three treatment techniques (photon, proton, and brachytherapy) as was done in the the NSABP B-39/RTOG 0413 national multi-institutional randomized control trial comparing APBI with WBI. The three techniques utilized are recognized as standard options for the delivery of APBI, and there is no evidence that any technique is superior to any other with commonly used dose and fractionation regimens.⁴ The primary endpoint is the difference from baseline in the percentage of patients with adverse cosmesis (fair or poor cosmesis) at 3 years. The intent is to determine whether the difference of adverse cosmesis rate is acceptable. Of interest is whether the 3 fraction accelerated APBI results in an unacceptable increase in the adverse cosmesis rate at the end of 3 years, compared to baseline. If it does not, then the 3 fraction accelerated APBI will be recommended for further study. If the change in adverse cosmesis rate is found to be unacceptable, then the recommendation would be to do no further studies of the 3 fraction accelerated APBI. In addition to adverse cosmesis, this study will assess many additional secondary endpoints including IBTR (both invasive and non-invasive IBTRs will be considered), acute and late toxicity profile, quality of life measures, and translational studies.

16.2 **Primary Endpoint:** The primary endpoint is the percentage difference in patients with adverse cosmesis (fair or poor cosmesis) at 3 years compared to baseline. Cosmesis will be assessed by a trained nurse provider using the Harvard Cosmesis Scale.

All patients meeting the eligibility criteria who have signed a consent form, and begun treatment will be considered evaluable for the primary endpoint.

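### The final analysis may start when the last patient has 24 months of follow-up, but the primary endpoint is cosmesis at 3 years

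*Combined protocol and SAP*

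**What the plan says.** Section 16.1 defines the outcome: "The primary endpoint is the difference from baseline in the percentage of patients with adverse cosmesis (fair or poor cosmesis) at 3 years". Sections 16.2 and 16.5 use the same time point.

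On timing, Section 16.44 says "Final analysis may begin approximately 5 years after the trial begins", and explains this as "as soon as the last patient registered has been observed for at least 24 months". The same section says "the accrual period for this study is expected to be approximately 3 years". It expects 5 patients a month in the first year, until the proton facility opens, "after which an accrual of 8 patients per month is anticipated".

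Section 16.8 gives a different milestone. The primary endpoint completion date "is at the time the last patient registered has been followed for at least 3 years", yet "the initial estimated completion date for the Primary Endpoint of this study is 5 years after the study opens to accrual".

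Section 16.5 places every eligible, consented woman who started treatment in the primary analysis. It takes the number with adverse cosmesis at 3 years, subtracts the number at baseline, "and then divided by total number of women in the primary analysis". It has no rule for a woman whose 3-year visit is not yet due.

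**The concern.** A final analysis at the earliest date 16.44 allows would be run before the most recently enrolled women could have a 3-year assessment. Sections 16.44 and 16.8 give different milestones, and only the one in 16.8 matches the endpoint. The early date is not an isolated slip, because 3 years of accrual plus 24 months is exactly the 5 years that 16.44 states.

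The decision is at stake. The 153 evaluable women were chosen so that an observed increase of 10 points has an upper bound at the 14% limit. With fewer assessed women, that precision is lost. If instead unassessed women stay in the denominator and add nothing to the 3-year count, the estimated increase shrinks and the rule tilts towards acceptable.

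**Working it through.** **Inputs.** Trigger 24 months, accrual about 36 months, calendar 60 months, rates 5 then 8 per month (16.44). 153 evaluable and 168 maximum (16.41). Assumed difference 10%, distance to the one-sided 95% upper bound 4 points, limit 14% (16.42). Annual visits to 5 years with a window of ±3 months (18.1), so a 3-year visit can fall at month 33. Adverse cosmesis in the cited randomized trial's APBI arm: 19% at baseline, 29% at 3 years (1.3.2).

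**The plan's own figures.**
- Calendar: 36 + 24 = 60 months, the stated 5 years.
- Sample size: n = 1.645² × 0.10 × 0.90 / 0.04² = 152.2, so 153; 153 + 15 = 168.
- Accrual: 60 + 8 × (T − 12) = 168 gives T = 25.5 months. The stated 3 years is not reproduced.

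**Women without the 3-year assessment at cut-off (of 168).** Even entry is assumed for the 36-month accrual.

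| Scenario | Visit at month 36 | All visits at month 33 |
|---|---|---|
| 36-month accrual, cut-off month 60 | 168 × 12/36 = 56 (33%) | 168 × 9/36 = 42 (25%) |
| Stated rates, 24-month trigger (25.5 + 24 = month 49.5) | 8 × 12 = 96 (57%) | 8 × 9 = 72 (43%) |
| Stated rates, waiting to month 60 | 8 × (25.5 − 24) = 12 (7%) | 0 |

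**Precision if only assessed women are analysed** (same variance assumed): distance = 4.0 × √(1/(1 − m)), where m is the unassessed share.
- m = 7%: about 142 of 153 women, 4.15 points
- m = 25%: about 115 women, 4.6 points
- m = 33%: 102 women, 4.9 points
- m = 57%: about 66 women, 6.1 points

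At m = 33%, an observed 10-point increase has an upper bound of 10 + 4.9 = 14.9%, above the limit.

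**Bias if 16.5 is read literally.** All treated women are in the denominator, all baseline events count, and visits not yet due add nothing at 3 years. The expected estimate is p₃(1 − m) − p₀. With p₀ = 0.19 and p₃ = 0.29, a true increase of 10 points:
- m = 7%: 0.29 × 0.929 − 0.19 = +7.9 points
- m = 25%: 0.29 × 0.75 − 0.19 = +2.75 points
- m = 33%: 0.29 × 0.667 − 0.19 = +0.3 points

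A milder reading also drops the baseline events of unassessed women but keeps these women in the denominator. The estimate is then 10 × (1 − m): +9.3, +7.5 and +6.7 points.

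**Can the decision reverse?** Take a true increase of 20 points, which 16.42 treats as unacceptably high, with p₀ = 0.19 and p₃ = 0.39 under the literal reading.
- m = 33%: 0.39 × 0.667 − 0.19 = +7.0 points, about 11/153. The exact one-sided 95% upper bound is 11.6%, below 14%.
- m = 25%: +10.25 points, about 16/153. The bound is 15.4%, above 14%.

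At the expected estimate, then, the decision reverses at one third unassessed but not at one quarter.

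**Calendar with a 36-month trigger.**
- 3-year accrual: 36 + 36 = 72 months (6.0 years), or 75 (6.25 years) once the last visit window has closed.
- Stated rates: 25.5 + 36 = 61.5 months (5.1 years), or 64.5 (5.4 years) with the window.

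**The case against.** Section 16.44 says the analysis may begin, not that it must, and 16.8 already holds the 3-year definition. A careful team would wait, and the data are delayed rather than lost. That is true, but 16.8 concerns results reporting, while 16.44 is the section that times the final analysis. A pre-specified trigger should not authorise a primary analysis before the endpoint is observable.

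The unassessed share depends on the accrual pattern. It runs from 0% to 57% across the scenarios above, and 25–33% needs even entry over 36 months. This stands, and the figure should always carry that condition. Likewise, the 5 years in 16.8 is nearly right at the stated monthly rates (5.1 years) and fails only if accrual takes 3 years.

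The accrual figures might be reconciled through the cap of 60 per arm. Brachytherapy at 13 per 3 months (4.33 a month) would fill its arm at about month 13.8, with about 75 women enrolled in total. If no one moved to another arm, the remaining 3.67 a month would reach 153 at about month 35 and 168 at about month 39. The trigger would then leave 33 to 44 of 168 unassessed (20–26%). The plan does not give this reasoning, and it replaces the stated 8 a month with 3.67. It shows how 3 years might have been reached, but not that the text is consistent. The share is still large.

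The largest bias figures come from one reading of 16.5. With assessed women only, this bias is absent and the cost is precision; the milder reading gives +6.7 rather than +0.3 points at 33%. This also stands: the bias is conditional, and it arises because 16.5 does not say which reading applies.

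**Conclusion.** The concern holds. The trigger in 16.44 is a year too early for the endpoint and disagrees with 16.8. With 3-year accrual and even entry, 25–33% of women (42 to 56 of 168) would lack the primary assessment at the earliest permitted analysis; the 15 women added for attrition cannot absorb that. At the stated monthly rates the literal trigger leaves 43–57% unassessed, while waiting for calendar year 5 leaves 0–7%. Ordinary loss to follow-up would come on top.

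The loss of precision follows whenever only assessed women are analysed. The bias towards acceptable follows only if unassessed women stay in the denominator; its size uses the cited trial's 19% and 29% as an illustration. The mismatch between the stated rates and the stated accrual period is a second, smaller inconsistency in the same section. This must be corrected before the analysis is run.

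**What to change.** In 16.44, replace 24 months with 36 months: the final analysis starts once the last patient's 3-year assessment is done or its +3-month window has closed. State one accrual assumption, by correcting either the 3-year period or the monthly rates; if the arm caps explain the difference, say so. Then give the same calendar figure in 16.44 and 16.8: about 6 years with 3-year accrual (6.25 with the window), or about 5.1 years at the stated rates (5.4 with the window).

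The cost is wording in two sections and time. The analysis moves 12 months after the present trigger, or up to 15 with the window. Against the stated calendar year 5 it is 12 to 15 months later with 3-year accrual, or 1.5 to 4.5 months later at the stated rates. No patients or visits are added, because the 3-year visit is already scheduled.

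This removes the problem of visits not yet due. It does not settle how 16.5 should treat 3-year assessments missing for other reasons, which needs its own rule.

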3.46 Extensive intraductal component

3.47 Active connective tissue disease

3.48 Reduction mammoplasty if 3DCRT or proton APBI are planned

3.49 Last surgery >10 weeks from enrollment

4.0 Test Schedule

Assessments, tests and procedures	Active Monitoring Phase				Observation
	Baseline ²	Radiation Treatment	Last day of radiation treatment (+/-2 days)	12 weeks (+/- 8 weeks) post-radiation	
History and Physical exam (including breast assessment/exam) ¹	X		X	X	X
Mammogram	X ¹¹				X ⁸
Consent	X				
Cosmetic and QOL Outcome Assessment (see section 11.3 and Appendix)	X		X	X	X
Digital Photograph	X ¹⁰		X	X	X
Histologic Assessment	X ³				
Radiation toxicity assessment (see section 10.4)	X		X	X	X
Serum pregnancy test	X ⁴				
Blood specimen ^{5,R}	X ¹²		X		
Clinically indicated treatment		X			

Surgical tumor specimen ^{6,R}	X ⁹				
----------------------------------------	----------------	--	--	--	--

1. A general clinical history & physical must be done \leq 8 weeks prior to registration. This should include assessment of ECOG performance status (see Appendix I).
2. Procedures done prior to radiation therapy.
3. Outside pathology must be reviewed at the treating institution.
4. For women of childbearing potential only
5. See section 14 for collection time and preparation of samples
6. See section 17 for collection time and preparation of samples
7. Patients that cannot come back to Mayo Rochester within the time constraints of the follow-up schedule; efforts to obtain outside records and send QOL's to be completed will occur however the specifics of the test schedule may not be captured. Observation will occur for a total of 5 years unless the patient goes off study.
8. As clinically indicated
9. Collect post-surgery
10. Ideally prior to surgery but can be done prior to radiation
11. Completed \leq 6 months prior to study entry
12. Radiation Oncology Registry and Biobank (IRB: 15-000136): Blood specimen is required to be collected prior to the start of radiation therapy.
- R. Research required testing

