13.0 Treatment/Follow-up Decision at Evaluation of Patient

13.1 Patients who have a recurrence while receiving therapy or during observation will go to the event-monitoring phase and be followed.

13.2 Patients who discontinue treatment or observation for reasons other than recurrence will go to the event-monitoring phase and be followed.

13.3 Patients that complete all adjuvant treatment will then be followed during the observation phase as outlined in section 4.0.

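### The primary estimator counts a woman with no 3-year cosmesis score as not adverse, so missing follow-up pushes the result toward acceptable

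*Combined protocol and SAP*

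**What the plan says.** Section 16.5 sets the analysis population: "All patients meeting the eligibility criteria who have signed a consent form and started treatment will be in the primary analysis". The numerator is the "number of women who had an adverse cosmesis event at 3 years minus number of women who had an adverse cosmesis event at baseline", and the denominator is every woman in that population. Section 16.2 calls the same women evaluable and does not require a 3-year score. The primary measure is a Harvard Cosmesis Scale rating by a trained nurse. The regimen passes if the upper confidence bound for the difference lies below 14% (sections 16.42 and 16.5).

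The documents contain no complete-case, imputation, carry-forward or sensitivity rule for a missing 3-year score. Section 18.23 asks only that missing form entries be explained.

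The plan itself foresees women without that score:

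- Section 13.1: "Patients who have a recurrence while receiving therapy or during observation will go to the event-monitoring phase and be followed". Section 13.2 does the same for women who stop treatment or observation for other reasons. The only form listed for event monitoring in section 18.1 records survival and disease status.
- Section 4.0, footnote 7, provides for "Patients that cannot come back to Mayo Rochester within the time constraints of the follow-up schedule". Outside records and mailed quality-of-life forms will be sought, but the footnote accepts that scheduled items may be lost.
- Section 16.44 lets the final analysis begin once the last patient has 24 months of observation, although section 16.8 defines primary completion at 3 years.

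On the accrual margin, section 16.41 says: "We anticipate accruing 15 additional patients to account for ineligibility, cancellation, major treatment violation, or other reasons".

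**The concern.** A difference between two counts is a valid change in rate only if both counts come from the same women. Here the baseline count covers everyone treated, while the 3-year count can cover only those who were scored. A missing woman who was good or excellent at baseline enters as unchanged. A missing woman who was fair or poor at baseline enters as −1, that is, as improved.

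The estimate drives a go/no-go rule on a harm endpoint, and worse follow-up makes that rule easier to pass. The accrual margin does not help, because a treated woman without a 3-year score still counts as evaluable. Women re-treated for recurrence may well have worse cosmesis and are among those moved out of scoring, but the bias does not depend on that: it arises even when scores are missing completely at random.

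**Working it through.** **The plan's own sample size.** Section 16.42 states: "A one-sided 95% confidence interval (with the upper bound of the interval) was computed". It assumes a 10% difference and 4 points from there to the upper bound. n = 1.645² × 0.10 × 0.90 / 0.04² = 152.2, rounded up to 153, which matches section 16.41. The whole design distance from expected value to margin is therefore 4 points.

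**Direction of the error.** Let A0 be the number adverse at baseline, and A3obs and A3mis the numbers truly adverse at 3 years among scored and unscored women.

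- Full data: (A3obs + A3mis − A0)/N
- As written: (A3obs − A0)/N
- Error: −A3mis/N, which is zero or negative whatever the reason for missingness.

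If a fraction m is missing at random, the expected estimate is (1 − m)·p3 − p0 and the bias is −m·p3.

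**Inputs.** N = 153 (16.41). p0 = 19% at baseline and 29% at 3 years in the cited external-beam APBI trial (section 1.3.2). Values of m are assumptions.

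**Worked case, m = 10%, p0 = 19%, p3 = 33% (true rise 14 points).** Adverse at baseline: 0.19 × 153 = 29.1. Truly adverse at 3 years: 0.33 × 153 = 50.5. Scored as adverse: 0.9 × 50.5 = 45.4. Estimate: (45.4 − 29.1)/153 = 10.7%, against a true 14.0%.

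**Decision probability.** The one-sided exact 95% bound on 14/153 is 13.9% and on 15/153 is 14.7%, so the rule passes at 14 or fewer net events. If no baseline-adverse woman improves, each woman contributes +1 with probability 0.14(1 − m), −1 with probability 0.19m, and 0 otherwise. Summing over 153 women gives the chance of passing at a true 14-point rise. The last column is the paired alternative, which drops unscored women from both counts and the denominator.

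| Missing | Expected estimate as written | P(pass) as written | P(pass) paired |
|---|---|---|---|
| 0% | 14.0 | 4.8% | 4.8% |
| 5% | 12.4 | 16% | 4.0% |
| 10% | 10.7 | 34% | 3.7% |
| 15% | 9.1 | 56% | 3.7% |
| 20% | 7.4 | 75% | 3.7% |

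**Sensitivity, true rise 14 points.**

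- Baseline 5% (assumed): 17%, 28% and 40% pass at 10%, 15% and 20% missing.
- Baseline 10% (assumed): 23%, 38% and 55%.
- Baseline 19%, with 5% of all women improving from adverse: 12% with none missing, then 38%, 55% and 71%. The paired rule stays at about 10%.
- Baseline 19%, bound read as two-sided (pass at 12 or fewer): 1.4% with none missing, 20% at 10% missing.

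**Analysis timing.** If analysis began 24 months after the last registration, women registered in the final 12 months of accrual would have under 36 months of follow-up. At the stated rates (5 per month for a year, then 8) that is 12 × 8 = 96 of 168, or 57%. With uniform accrual over 36 months it is 12/36 = 33%. Allowing the 3-month visit window in section 18.1 gives 72/168 = 43% and 9/36 = 25%.

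**The case against.** The plan never says in words that missing means not adverse. It is silent, and a statistician might in practice use complete cases or the last annual score. That is true, but either choice would depart from the stated population or add an unstated rule after data are in hand. The formula as printed gives the biased result.

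The size is uncertain. The 19% baseline comes from a different trial and regimen, and no dropout rate is given. Recurrence alone would remove few women: local failure in the APBI series cited in section 1.2 is mostly about 1–6% at 4–7 years. At 2–3% missing, the pass rate at the margin rises only to about 8–11% with a 19% baseline and 6–7% with a 5% baseline. Inclusion criterion 3.24 requires willingness to return, which should limit loss. All this stands and bears on magnitude, not direction. Outside records and mailed questionnaires do not supply a nurse-rated score.

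A missing baseline score would bias the other way. That also stands, though it should be rarer because baseline scoring precedes treatment.

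A paired complete-case analysis removes the bias only if loss is unrelated to cosmesis. This stands, and is why sensitivity analyses are needed beside it.

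Finally, the 4.8% reference follows from the stated decision rule, not from the operating-characteristics table in section 16.42. That table gives 48.6% at a true 15% increase, where the exact rule gives 2.3%. The table does not reproduce; that is a separate matter.

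**Conclusion.** The concern holds. The estimator in section 16.5, applied as written, can only understate the increase when 3-year scores are missing, and the plan creates women without scores. Under the 19% baseline, 10% missing costs about 3 of the 4 points between the design value and the margin (2.9 points if the 3-year rate is 29%, 3.3 if it is 33%). At a true 14-point rise, the chance of a false acceptable conclusion goes from about 5% to about 34%; with an assumed 5% baseline it goes to 17%. These figures rest on assumed missing fractions, random missingness, no improvers and a one-sided exact bound. Relaxing the last two, or lowering the baseline, changes the size but not the direction. Because this one estimate decides the trial's conclusion, it should be corrected before analysis.

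**What to change.** Amend section 16.5 so that both counts and the denominator use the same women: those eligible and treated who have both a baseline and a 3-year Harvard score. State the 3-year visit window, and reconcile the 24-month analysis start in section 16.44 with the 3-year completion definition in section 16.8.

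Pre-specify two sensitivity analyses on all eligible treated women: multiple imputation of the 3-year score from baseline and interim cosmesis scores already collected, and missing counted as adverse. Report the number missing, with reasons (death, recurrence, withdrawal, unable to return), and say how the conclusion is worded if the analyses disagree.

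The cost is SAP wording and modest programming; no new data are needed. The paired set may fall below 153. With 10% missing, the one-sided half-width at a 10% difference grows from 4.0 to 1.645 × √(0.09/137.7) = 4.2 points. Under the exact rule, the chance of passing at a true 10-point rise falls from 43% to about 35%. The 15 extra women cover at most 15/168 = 8.9% loss from all causes, so the accrual target should be checked against expected loss of 3-year scores.
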